#### 468 **V. Month 6 and Month 12 Testing (Times 2 and Time 3)**

469 During months 6 and 12, while estradiol is still on board but before the quarterly dose of  
470 micronized progesterone is administered, all procedures described above for pre-treatment (Time  
471 1) testing will be repeated, ensuring that the participant is wearing a patch at the time of testing.  
472 At the end of the 12 month, Time 3 testing women will be abruptly withdrawn from the  
473 intervention since in the majority of women, there is no definitive evidence that tapering the  
474 discontinuation of ERT is associated with fewer vasomotor symptoms in the majority of women  
475 (Aslan E, et al., *Maturitas*. 2007 Jan 20;56(1):78-83. Epub 2006 Oct 13; Grady D et al., *Am J*  
476 *Med*. 2005 Dec 19;118 Suppl 12B:163-5).

477

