#### 60 **Changes made to study protocol:**

- 61 • Rather than starting a participant on 0.1 mg of estradiol immediately, the protocol was  
62 changed so that participants started on 0.025 mg for two weeks, then 0.05 mg patch for the  
63 next four weeks, and a 0.1 mg patch for the remainder of the study **(2011-02-14)**.
- 64 • To avoid very heavy bleeding following progesterone administration, the schedule for  
65 administering progesterone was changed from every three months to every two months  
66 **(2011-07-08)**.
- 67 • Participant compensation was increased to \$1325 when study visits at months 6 and 12  
68 began occurring separately from the months 6 and 12 laboratory visits **(2012-05-15)**.
- 69 • Following randomization, participants were given the option to participate in four follow-up  
70 phone calls in which the CES-D was administered (months 15, 18, 21 and 24) for an  
71 additional \$100 in compensation **(2012-05-15)**.

72

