## 102 **Purpose and Rationale**

103 The following are the driving assumptions of this study:

104 **1. Depression and CVD display reciprocal risks:** Both animal and human studies demonstrate  
105 a strong link between DEP – a major source of morbidity – and CVD – the leading killer of  
106 women in the US. Patients with CVD are more likely to develop DEP (e.g., the prevalence of  
107 DEP in patients with congestive heart failure reportedly reaches 40%);, and conversely, the  
108 presence of DEP in patients with CVD predicts increased morbidity and mortality. This risk  
109 applies as well to women with depressive symptoms (50% greater likelihood of dying a cardiac  
110 death) and even euthymic individuals with a history of DEP (see below).

111 **2. The risk of DEP and CVD increases during the perimenopause:** Although age is likely the  
112 major cause of the rapid increase in the incidence of CVD in PM women, the importance of  
113 estradiol in CV risk is supported by the substantial increase in CVD in women undergoing early  
114 menopause, oophorectomy without estrogen replacement, or premature ovarian failure, a disorder  
115 associated with impaired endothelial function and increased CV mortality. Studies in  
116 cynomolgus macaques also demonstrate that impaired ovarian function is associated with  
117 extensive coronary atherosclerosis. Thus, loss of estrogen appears to contribute to the higher  
118 incidence of CVD morbidity and mortality in older women. Studies have demonstrated at least  
119 a twofold increase in depression in women during the perimenopause, and our group has shown  
120 that estrogen withdrawal precipitates depression in women on hormone replacement therapy  
121 (HRT) (combined estrogen plus progestin) with a history of perimenopausal depression.

122 **3. Depression, CVD, and estrogen deficiency share common pathophysiologic**  
123 **perturbations, which collectively constitute a risk profile for CVD and depression.** These  
124 include the following: 1) Immune activation and inflammation; 2) Endothelial dysfunction; 3)  
125 Cardiac Autonomic Dysregulation; and 4) Metabolic Risk. It is well established that each of  
126 these factors predicts CVD and, as well, is associated with both depression and post-menopausal  
127 status.

128 **4. A past history of depression, and factors that lead to depression (traumatic events),**  

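### The last mandatory mood and adverse event check comes before abrupt estradiol withdrawal and the final capsule course; after it only call-in and optional CES-D calls from month 15 are stated

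*Protocol*

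**What the plan says.** **Order of events at month 12.** Protocol section IV (12 Month Intervention Phase) places every visit in the first half of the month, ahead of the capsules. Its paragraph on progesterone puts the blinded capsules in the last 12 days of each month. Section V times the laboratory sessions "During months 6 and 12, while estradiol is still on board but before the quarterly dose of" progesterone, with a patch on. It then says "At the end of the 12 month, Time 3 testing women will be abruptly withdrawn from the" intervention. The only reason given for stopping abruptly concerns hot-flush-type symptoms: the section finds no firm evidence that tapering the "discontinuation of ERT is associated with fewer vasomotor symptoms in the majority of women".

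**Later changes.** Under Changes made to study protocol, the month 6 and 12 study visits "began occurring separately from the months 6 and 12 laboratory visits", with no visit added after treatment stops. Progesterone was moved from three-monthly to two-monthly: "To avoid very heavy bleeding following progesterone administration, the schedule for" giving it was changed. From 15 May 2012, "Following randomization, participants were given the option to participate in four follow-up" "phone calls in which the CES-D was administered (months 15, 18, 21 and 24) for an" extra $100.

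**The hazard.** Purpose and Rationale, item 2, reports from the investigators' own group "that estrogen withdrawal precipitates depression in women on hormone replacement therapy" and a history of perimenopausal depression. Item 5 repeats this and adds that women without that history did not show it.

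**Other safeguards.** Protection Against Risk describes a sheet telling women to call the study doctors about listed symptoms. Monitoring and Reporting of Adverse Events ties side-effect monitoring to study visits. It requires immediate reporting of a CES-D above 10, of suicidal ideation, or of mood deterioration reported by telephone.

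**The concern.** The protocol names stopping estradiol as a trigger of depression, and half its sample is recruited for recurrent depression. Its stated protection against undetected mood deterioration is frequent contact and assessment, and that protection ends at month 12, just before the trigger is applied. The final progesterone course also falls after the last check, although bleeding after progesterone was troublesome enough to change the schedule.

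Within the document, then, a withdrawal episode or bleeding after the last course is found only if the woman phones in. For mood, it may also be found if she accepted the optional calls and the episode is still present, or has returned, when she is called. A woman who is becoming depressed may not phone. What is at stake is participant safety, not the estimate of the treatment effect.

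**Working it through.** The plan states no figure to reproduce. The check is the order of events and calendar arithmetic, in elapsed months with 30-day months.

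**1. Is the last mandatory check before both events?**
- Month 12 visit: days 1 to 14 (section IV). Capsules: last 12 days, days 19 to 30.
- Visit to last capsule: 30 − 14 = 16 days to 30 − 1 = 29 days. The visit always comes first.
- The Overview of Protocol speaks of the end of month 12 for testing, but also places it before the final progesterone, so the order is the same.
- Testing is done with a patch on, and withdrawal follows it.

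**2. Gap from last patch to first optional call.** The month 12 visit falls at 11.0 to 11.5. Assume the month 15 call is timed like a visit, at 14.0 to 14.5.
- Patch stopped at testing: 14.0 − 11.5 = 2.5 to 14.5 − 11.0 = 3.5 months.
- Patch stopped at the end of month 12: 14.0 − 12.0 = 2.0 to 14.5 − 12.0 = 2.5 months.
- Together: 2.0 to 3.5 months.
- Measured instead from the last mandatory check, with the call anywhere in month 15: 16 + 60 + 1 = 77 days to 29 + 90 = 119 days.
- For comparison, scheduled checks on treatment (months 0, 1, 2, 4, 6, 8, 10, 12) are 1, 1, 2, 2, 2, 2 and 2 months apart.

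**3. Progesterone courses followed by a scheduled visit.**
- Three-monthly: month 3 to visit 4 and month 9 to visit 10, 0 to 2 weeks; month 6 to visit 8, about 4 to 6 weeks; month 12, none. That is 3 of 4.
- Two-monthly, assuming even months: months 2, 4, 6, 8 and 10 to the next visit, about 4 to 6 weeks; month 12, none. That is 5 of 6.
- Only the last course has no later visit, on either schedule.

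**4. Number of women.**
- Assigned to estradiol: 160 (section III). With recurrent depression: 160 / 2 = 80. Both are maxima before attrition.
- If the 240 subjects in the power calculation are completers, which the protocol does not say: 240 / 320 = 0.75, giving 160 × 0.75 = 120 and 80 × 0.75 = 60.
- With a history of perimenopausal depression: not stated. Within the recurrent-depression stratum on estradiol it could be anything from 0 to 80.

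**5. Would moving the month 15 call forward do?**
- A call 4 to 6 weeks after the capsules end (12.0) falls at 12.0 + 28/30 = 12.9 to 12.0 + 42/30 = 13.4. The month 18 call, timed like a visit, is at 17.0 to 17.5.
- Gap without a month 15 call: 17.0 − 13.4 = 3.6 to 17.5 − 12.9 = 4.6 months, longer than the 2.0 to 3.5 months at issue.
- The early call therefore has to be added, not exchanged.

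**6. Cost.** $100 / 4 calls = $25 per call if split evenly, the same as an interim visit under Inducements for Participation. $25 × 320 = $8,000; $25 × 240 = $6,000.

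**The case against.** **The hazard is stated for a different group.** Rationale item 5 limits withdrawal depression to women with past perimenopausal depression; the trial recruits for recurrent depression in remission. This stands. A reader might infer that 80 or even 160 women are at risk. The documents do not support that: those are upper limits on who stops estradiol, and no event rate is given.

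**Women are not left without cover.** The sheet lists depression, suicidal thoughts and heavy or lasting bleeding, staff must escalate what reaches them, and paid calls are offered. This also stands, so it would be wrong to say that there is no safety net. But the sheet is passive, the document does not say whether it applies after treatment ends, and the calls are optional, late and described only as CES-D administration. Women who declined them, or finished before 15 May 2012, have no active contact stated. A CES-D above 10 at month 12 can prompt reassessment two weeks later, but that score precedes withdrawal. The one-year mammogram checks neither mood nor bleeding.

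**Exit instructions may sit in papers not shown**, such as the consent form or the sheet itself. That is possible and lowers confidence; it does not show that a contact exists.

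**The split month 12 visit has no stated order.** True, but section IV applies its rule to all visits, and the change added none after withdrawal.

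**The bleeding argument is modest.** The schedule change is already a mitigation, and no bleeding rate after it is given. It supports including bleeding in a call, not a claim of a known residual risk.

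A reader might also infer that abrupt stopping is itself wrong, or that the treatment comparison is biased. Neither follows. The protocol gives no evidence that tapering would prevent depression, and the stated Aim 2 and 3 hypotheses run over 12 months.

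**Conclusion.** The point holds as a limited safety gap. The last mandatory CES-D and adverse event check precedes both estradiol withdrawal and the final capsule course. Active contact after it is optional and starts about 2.0 to 3.5 months after the last patch. That range assumes the month 15 call is timed like a visit, with the last patch coming off between testing and the end of month 12.

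At most 160 women stop estradiol and at most 80 of these have recurrent depression; the number to whom the protocol's own warning applies is unknown. No event rate, power or error-rate effect, or bias is claimed. It is best classed as a cheap improvement. Confidence is medium, because part of the case rests on what this document does not state.

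**What to change.** Add one mandatory telephone contact in both arms, made blind to treatment, about 4 to 6 weeks after the last patch and capsule. Cover the CES-D, adverse events and bleeding. Apply the existing escalation in Monitoring and Reporting of Adverse Events for a CES-D above 10 or suicidal ideation. Keep the optional calls at months 15, 18, 21 and 24 as they are.

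The 4 to 6 weeks is a practical choice: it matches the longest interval the schedule leaves between a non-final progesterone course and the next visit. The documents give no time course for withdrawal depression, so it cannot be presented as the best time to detect it.

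Cost: a protocol amendment and one more short contact per woman by existing staff, about $25 each if priced like the optional calls. That is at most about $8,000 for 320 women, or $6,000 if 240 complete. No planned time point is lost.

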### 478 **MEASUREMENTS**

#### 479 **Cardiovascular Risk Measures**

480**1) Metabolic Risk:** We will employ National Cholesterol Education Program (NCEP) standard  
481 criteria for determining the Metabolic Syndrome based on blood pressure (BP) levels, abdominal  
482 obesity, and fasting triglyceride, HDL and glucose. For **BP:** subjects will be seated for 5 mins  
483 with arm supported at heart level. The auscultatory method will be used, employing a hand  
484 aneroid sphygmomanometer and stethoscope placed over the brachial artery at the inside of the  
485 elbow. A minimum of two BP measurements will be taken at least 5 mins apart and averaged to  
486 determine BP. **Waist Circumference** will be measured using the NHANES III Protocol . The  
487 subject stands and the examiner palpates the upper hip bone to locate the right iliac crest to  
488 determine the mid-axillary line. The measuring tape is placed in a horizontal plane around the  
489 abdomen at this point and the measure is made at a normal minimal respiration. Following an  
490 overnight fast, blood will be sampled for **fasting triglycerides and HDL** (see assay descriptions  
491 below). We will also use **Insulin Sensitivity/Resistance to assess metabolic risk** using  
492 Homeostasis Model Assessment (HOMA) beta-cell index derived from a single fasting sample of  
493 glucose and insulin levels. This is the most widely used surrogate measure of insulin resistance  
494 (IR). Fasting HOMA-IR levels have been shown in large scale studies to predict CV events even  
495 after adjustment for other traditional risk factors. We will use the standard calculation for  
496 HOMA-IR, which is fasting insulin (uU/ml) times fasting glucose (mmol/l) divided by 22.5.  
497 Homa-IR has been validated in normoglycemic subjects against insulin sensitivity measured  
498 directly from the euglycemic-hyperinsulinemic clamp technique. Subjects will be considered  
499 insulin resistant on the basis of HOMA-IR > 3.2, consistent with other investigations.

500

501 **Metabolic Risk will be assessed at baseline, month 6 and month 12. Subjects will be**  
502 **classified as having metabolic risk if they either:** 1) meet standard NCEP criteria for  
503 metabolic syndrome based on any three of the following risk factors: (1) BP  $\geq$ 130/  $\geq$ 85 mmHg,  
504 (2) waist circumference  $>$  88 cm, (3) triglycerides  $\geq$  150 mg/dl, (4) HDL cholesterol  $<$  50 mg/dl,  
505 and (5) fasting glucose  $\geq$  110 mg/dl.; **or 2)** are insulin resistant, a clear metabolic predictor of  
506 CVD, i.e., if their HOMA-IR is  $>$  3.2. **2) Sequence Technique for estimating Baroreflex**  
507 **Sensitivity:** 5-min recording of BP and RR interval will be scanned for sequences in which SBP  
508 and the subsequent RR interval progressively increase or decrease over 3 consecutive beats.  
509 Sequences will be selected if successive pressure pulses differ by at least 1.0 mm Hg and  
510 successive RR intervals differ by at least 5.0 msec. Linear regression relating RR interval to  
511 SBP will be plotted for each sequence, and the slope of the function will be the estimate of BRS.  
512 Slopes derived from all sequences will be pooled so that one measures of baroreceptor sensitivity  
513 will be obtained. 3) **Blood Pressure and Vascular Resistance Reactivity to Stress:** The  
514 Suntech Exercise BP monitor, Model 4240 (SunTech Medical Instruments, Inc., Raleigh, NC),  
515 will provide automated measurement of BP during stress testing using the auscultatory  
516 technique. Initially, five standard stethoscopic BPs will be taken simultaneously with the  
517 automated pressures in order to insure correct microphone placement and cuff positioning.  
518 Impedance cardiography is noninvasive and involves recording changes in thoracic impedance  
519 by use of a tetrapolar electrode system, together with a standard ECG. Impedance cardiography  
520 has been extensively evaluated by comparison with traditional invasive techniques in human and  
521 animal studies. For each min of interest, a 30-s continuous sample of waveforms (obtained  
522 concurrently with BP) will be processed to generate an ensemble-averaged cardiac cycle, from  
523 which stroke volume will be determined and HR will be determined by the interbeat interval.  
524 Cardiac output and total peripheral resistance are calculated using standard formulae. To control  
525 for differences in BMI, measures will be adjusted for body surface area, yielding indexed scores  
526 (e.g. vascular resistance index (VRI)). **Flow Mediated Dilatation:** Digital gated images of the  
527 brachial artery will be acquired for analyses. Measurements will be performed using customized  
528 software (Vascular Analysis Tools, Medical Imaging Applications, LLC). Arterial diameter will  
529 be quantified by analysis of each image sequence, measuring from the intima-lumen interfaces of  
530 the proximal and distal arterial walls. Baseline resting arterial diameters will be quantified as the  
531 average of measurements on 10 or more images. Arterial diameters during reactive hyperemia  
532 and following nitroglycerin administration will be calculated as the average of measurements on  
533 3 consecutive images at maximum dilatation. Flow mediated and nitroglycerin-mediated  
534 dilatation will be expressed as percent changes in diameter relative to resting scans.

### 535 **Affective Well-Being Measures**

536 **1. Depression Episodes** will be operationalized in a manner consistent with other studies in  
537 perimenopausal depression and based on the following assessments: **The Center for**  
538 **Epidemiologic Studies Depression scale (CES-D)** is a 20-item self-report form assessing  
539 depressed mood. CES-D scores  $\geq$  16 have been consistently validated as defining high  
540 depressive symptoms suggestive of clinically significant DEP (positive predictive value=75%),  
541 and this cut-point has been used to define depressive episodes in multiple perimenopausal  
542 samples. Moreover, elevated CES-D scores have been shown to be sensitive to the anti-  
543 depressant actions of ERT in PM women. **Thus, CES-D scores  $\geq$  16 will be used to**  
544 **operationally define ‘depression episodes’.** However, if CES-D scores are  $>$  10 at any study  
545 visit then the Structured Clinical Interview for DSM-IV (non-patient edition) will be

546 administered to determine the presence of either minor or major depression. **Functional**  
547 **Impairment:** We will use the widely used Medical Outcomes Study 36-item short form (SF-  
548 36), which yields scores of general health perceptions, physical functioning, role limitations due  
549 to physical functioning, social functioning, bodily pain, general mental health, role limitations  
550 due to emotional problems, and vitality. The rationale for the selection of this instrument is  
551 based on: 1) the demonstration that it is sensitive to change over time; 2) its incorporation of  
552 subscales to specifically assess functional impairment related to emotional and physical  
553 symptoms as well as overall social functioning; 3) its able to discriminate subgroups of CVD  
554 patients known to have poorer survival and worse disease; and 4) normative data for this scale  
555 are available for the general US population as well as 13 medical conditions. **Symptom**  
556 **Severity and Affective Instability** will be assessed with the CES-D scale (at baseline and  
557 months 2,4,6,8,10 and 12), the former with a repeated measures approach and the latter by the  
558 variance in the CES-D score over 12 months.

559 **Lifetime Trauma Exposure** will be assessed by a validated interview. A cumulative (total)  
560 trauma score will be generated by assigning one-point for each of the following 15 traumas: **1)**  
561 history of sexual abuse; **2)** history of physical abuse; **3)** moderate or greater childhood physical  
562 neglect; **4)** moderate or greater childhood emotional neglect; **5)** presence of 7 other types of  
563 trauma (one point each) before the age of 18; **6)** presence of 4 lifetime traumas (1 point each).  
564 The measure of lifetime *sexual and physical abuse history* is based on previous studies by  
565 Investigator, [name], and adapted from other research. Cumulative trauma exposure has  
566 been shown to independently predict the development of adverse medical conditions, to be  
567 related to a variety of risk factors for the leading causes of death; and to predict CV reactivity to  
568 acute laboratory stressors.

#### 569 **Benefits to Subjects and/or Society**

570 Subjects randomized to active ERT may experience a direct benefit, as treatment may reduce  
571 depressive episodes, improve quality of life, and reduce cardiovascular risk. The benefits to all  
572 subjects also include study-related medical evaluations, including a gynecological exam and  
573 mammograms. Subjects may also benefit by knowing that they are contributing to research  
574 aimed at enhancing our understanding of depression and cardiovascular risk in perimenopausal  
575 women. Even women who are excluded from participating based on medical or psychiatric  
576 criteria are intended to benefit to some degree since they will receive valuable feedback on their  
577 current medical and psychiatric status and referral for treatment when indicated. Society may  
578 benefit if this study yields knowledge on predictors of ERT benefit in perimenopausal women.

#### 579 **Risks and Measures to Minimize Risks**

580 The most likely risks involve side effects associated with the use of reproductive hormones  
581 (estradiol or progesterone).

582 The most frequent side effects associated with estradiol use include edema, breast tenderness,  
583 and changes in appetite and weight. Less frequent side effects include jaundice, nausea,  
584 abdominal cramps, increased blood pressure, headache and worsening of migraines or asthma,  
585 depression, nervousness, acne, cystitis-like syndrome, enlargement of uterine fibroids,  
586 intolerance to contact lenses and dizziness. Skin rash or irritation may also occur at site where  
587 the patch (containing estrogen) is placed. Progesterone - The most common side effects

588 associated with progesterone include breast tenderness, dizziness, abdominal bloating, vaginal  
589 discharge, chest pain, and diarrhea. Less common side effects include headache, dizziness,  
590 breast pain, musculoskeletal pain, and viral infection

